improvement training packages that will be delivered to more than 350 healthcare providers in 60 healthcare facilities in this program, with an appropriate performance framework to follow-up key-indicators around ANC-PNC, with regard to HIV, TB and malaria in particular.

Overall, with 6,936 ANC visits (of which 3,248 attending for the first/booking visit) and 826 PNC visits in the month of the survey – giving an estimate of 93,144 women annually – there is a wide scope for reaching a substantial population of women and babies to provide them with both basic services and disease-specific care.

There was good availability of services reported for the three diseases; 90% facilities offered HIV screening and 78.3% also offered treatment; 91.7% healthcare facilities offered malaria screening and treatment; 35% offered TB screening and treatment. However, it was evidenced that despite the full availability of rapid diagnostic tests for HIV (100%), the systematic screening for HIV in ANC was incomplete: HIV tests were conducted for 2,501 women at ANC (1,791 among them at booking visit – 55% of all women coming for ANC1) and 237 (28.7%) at PNC. Besides, 15.5% of women were tested for syphilis at ANC1, and none at PNC, even though 60% of healthcare facilities had rapid diagnostic tests. Furthermore, there was no screening for TB in ANC or PNC (1 woman - ~0%), suggesting that there are missed opportunities for identifying positive cases linked to the clinical screening and the decision to test women. For malaria, 413 (12.5%) women were tested for malaria at ANC and 17 (2.1%) at PNC with all those testing positive starting treatment. The high positivity rate among women tested (47.5%), suggested that the low proportion of women tested in ANC and especially in PNC could result in missed opportunities to identify and treat women. Again, there was a reported good availability of malaria testing kits (80%), therefore ruling out lack of availability as a sole explanation for this. Regarding provision of intermittent preventive treatment of malaria in pregnancy (IPTp), 54% of eligible women received prophylaxis in ANC, despite Sulfadoxine-pyrimethamine (SP) being found in 94.3% of healthcare facilities. This is indicative of the opportunity to improve the provision of basic and disease specific care.

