3.1 Trial setting

3.1.1 Selection of participating HCFs

In consultation with the Ministry of Health public or private HCFs in N'Djamena have been identified. The facilities are: 1) designated to provide ANC and PNC, and 2) in a state of readiness to provide ANC and PNC (i.e. equipment and consumables in principle in place).

The above criteria will be observed to provide a sample of primary and secondary or above healthcare facilities to include all levels of service provision. Based on the previous engagement in Chad, of the 20 HCF from N'djamena included in the initial facility assessment, at least 18 will be included in the trial. There will be a possibility to include up to 20 HCF, depending on advice from the Ministry of Public Health, to balance the risk of attrition should any HCF from the sample decide to withdraw during the trial. All sample size calculation (see relevant sections below) assumed 18 HCFs, hence our calculation is conservative as a larger sample would only reduce the difference detectable. The current list of HCFs is provided in **Appendix 4**.

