3.4 Outcomes

This trial will have two primary outcomes, one around essential components for ANC, and one for essential components for PNC.

Outcome 1 (ANC): Essential components included in the composite measure of integrated services specific to ANC visits are listed below.

- EC1 = Respectful maternity care indicators:
 - Introductions, greeting the woman, consent, questions
- EC2 = Screening for Pre-eclampsia:
 - Measure BP

- Test urine for proteinuria
- EC3 = Screening for, prevention and management of Anaemia:
 - Measure Haemoglobin
 - Provide ferrous sulphate with folic acid
- EC4 = Screening for, prevention and management of Malaria:
 - Checked for clinical symptoms and test for Malaria if relevant
 - Provide treatment if needed
 - Provide bed nets if not provided yet
 - Provide Intermittent Presumptive treatment
- EC5 = Screening for, prevention and management of HIV:
 - Test for HIV
 - Provide Prevention of mother to child transmission care (PMTCT)
 - Provide anti-retroviral drugs (ARV) for mother if needed
- EC6 = Screening for, prevention and management of Syphilis:
 - Test for syphilis
 - Provide antibiotics if needed
- EC7 = Screening for, prevention and management of Tuberculosis (TB):
 - Checked for clinical symptoms and test for TB
 - First line TB drugs or referral if needed
- EC8 = Prevention of Tetanus in mother:
 - Tetanus toxoid vaccination
- EC9 = Screening and counselling for mental health and domestic violence:
 - Screening tools
 - Counselling services
- EC10 = Estimation of BMI:
 - Assess maternal height
 - Assess maternal weight
- EC11 = Prevention of post- and pre-term birth:
 - Estimate gestational age
- EC12 = Assessment of foetal wellbeing during pregnancy, Screening for multiple pregnancy, abnormal lie and presentation during pregnancy:
 - Assess growth using fundal height measurement
 - Assess foetal heart rate (FHR)
 - Abdominal palpation
- EC13 = Provide advice on birth preparedness and danger signs of pregnancy:
 - Consultation

The outcome for each ANC visit will be a score which measures the proportion of the above components that was delivered during that visit (EC_ANC).

The score will measure the proportion of essential components delivered in full. All thirteen essential components listed above are applicable for ANC. Some essential components

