All participants will be given the opportunity to ask questions, which will be fully answered. Due to the nature of the observation, time given for decision-making may be limited, but care will be taken to minimise any pressure for considering whether to participate from the women. To allow the women time to consider participating to the study, information will be given at different point of contact in the facility whenever possible, such as during registration or health promotion sessions. They will be allowed as long as they wish to decide and should have all the waiting time to reflect. Due to the usual capacity of healthcare facilities in Chad, ANC-PNC are usually crowded with women waiting a long time, and consultation kept short. All women will be informed that they can take time and decide later to be observed, however, there is a low chance that any would find worth to leave and come another day for the visit, due to the time and resources consumed. For women who may not be able to read and write, consenting will take place with the assistance of an independent witness.

The total number of HCPs to be trained and observed will be up to 54. At each HCF up to 12 women will be observed in each of four assessment periods. Thus, the total number of women asked to consent to be observed will be between 576 and 864.

Information on the availability of equipment and consumables for ANC-PNC components under assessment, will be retrieved from routine data records and directly from HCP. This step will therefore not require obtaining client consent.

Voluntary participation and right to withdraw

The head of the facility, healthcare providers, for observation and retrieval of information from patient-held records, will be informed of the voluntary participation and their right to withdraw without any consequences.

Clients for observation will be informed of the voluntary participation and their right to withdraw at any time during the observation without any consequences. However, it will not be possible to retrieve data once fully anonymised.

Confidentiality and anonymity

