Observation of each HCP in multiple assessment periods will improve the power of the trial to detect an improvement in outcomes, since underlying differences between individual HCPs will be able to be modelled using random HCP effects. However, shift patterns will limit the availability of participating HCPs, so at some HCFs it may be necessary to conduct observations on two different dates within a step to be able to observe at least two HCPs in each assessment period. In facilities where both ANC and PNC clients are seen by each participating HCP observations for both primary outcomes will be able to be completed using the same HCPs. For other facilities, where ANC and PNC clinics are completed by different sets of staff on any given shift it may be preferable to recruit 4 to 6 HCPs, some to be observed providing ANC and others PNC. This would enable HCPs in both clinics to be observed on some observation days, thereby reducing the number of observation days in the assessment period. **Box 2** summarises the sample size planned.

Each interaction (ANC and PNC) observed will be assessed for the corresponding primary outcome.

The R shiny app ($\frac{\text{Hemming}}{\text{Memming}}$, 2019) was used in February 2020 to perform power calculations for this design, using a continuous response, with a standard deviation of σ . The standard deviation, σ , is the square root of the total variance, which aggregates the various components of variance. The app is not designed for the additional level of observation within HCP, so the data considered for purposes of sample size calculation is the mean across four observations for each HCP at the HCF.

Box 2: Sample size details

Number of clusters (HCFs):	18
Number of steps:	6 (8 assessment periods)
Duration of steps:	6-7 weeks
For each HCF:	
Number of HCPs per primary outcome*:	3 (or 2)
Number of periods in which care at HCF is assessed:	4
	(periods 1, 3, 5 and 7
	or 2, 4, 6 and 8)
Number of HCPs assessed for each primary outcome per assessment period:	At least 2
Number of HCP-client interactions assessed for each primary outcome per HCP assessed in an assessment period	4

^{*} where clinics combine ANC and PNC clients the same HCPs can be used for both; where ANC and PNC clinics are separate different sets of HCPs may be used.

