3.7 Data collection

Data sources

The main sources of information will include:

1. Observation of ANC-PNC visits for assessment of delivery of care. The tools will be developed ahead of the trial start. Following consultation with in-country partners, they will be converted onto a standardised platform (paper or electronic) for use for data collection.

All data collection will be undertaken by clinically trained data collectors external to the HCF with supervision from CSSI-CRASH and remote support from LSTM. To enhance acceptability of observations and minimize any potential unease for the women to be observed, the data collectors will be exclusively females. Data collectors will receive training on data retrieval and collection; with regard to observation of ANC-PNC visits, specific training on research methods covering consenting, ethical aspects of observation, data anonymization, rapport building, and observation techniques will be provided. As specified in this document, data collection will take place at specified time points. For the observation, we expect data be collected for 4 consecutive clients coming for ANC per HCP observed for ANC and the same for PNC. In each assessment period there would be a total of 8 to 12 clients per facility for each consultation type (through as many visits as needed to observe 2 to 3 HCPs per facility). The data collection tools will therefore aim to capture the service provision of the HCP observed. Anonymous ID codes within HCF will be agreed and applied in the final database for each HCP observed.

2. Healthcare facility records and register review for extracting data on equipment, consumables, medications as well as elements of infrastructure availability, staff availability (by cadres and type of services provided; though no personal details of individual staff members), and uptake of services (number of women attending for ANC and PNC services, morbidities and mortalities related to pregnancy and childbirth, specific aspects of care provisions (all as pooled data for a specified month, with no individual details extracted).

Data collection

Before commencing either intervention the HCFs selected to participate in the trial will be surveyed to ascertain the availability of human resources and the components identified as in principle needed for the delivery of the essential components defined.

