Delivery of essential components will be assessed through the observation of ANC-PNC visits by external data collectors. At each healthcare facility at least two healthcare providers will be observed in each assessment period. For each assessment period one observation day will be scheduled for each HCF to be assessed in the period. All participating HCPs on duty within the HCF will be observed completing four ANC/PNC visits on each of these days. If only one participating HCP is observed an additional observation day will be scheduled within the same assessment period to observe at least one more participating HCP within the HCF. Each HCP should be observed in at least three of the four assessment periods for their HCF. The observers will plan with the healthcare facilities to observe four consultations for each HCP who is on duty in accordance to rosters.

The availability of equipment and consumables for each component of care for ANC-PNC services quarterly (every 2 steps in the trial schedule) will be assessed on the first possible day of the following quarter. This data will allow for the analysis to assess if the delivery of essential components was linked or not by the availability of equipment and consumables. Finally, the number of women attending for and receiving care will be extracted quarterly

using the official routine facility registers. The healthcare facility assessment tool for equipment, consumables and use of services has been developed in line with the specific ANC-PNC service provision elements and with usual facility assessment tools used by CMNH-LSTM in baseline assessment (See **Appendix 3**).

Covid-19 situation

As of 13th of May, borders are closed and international flight barred, public transportation interrupted and meetings of 50 people or more prohibited. Our focal point from MoH and implementation partners from CSSI-CRASH consortium have so far not advised against conducting the study, which will be set only within N'Djamena and thus not require any interregional travels that may be impeded in the future. To date no other measures that could impede the delivery of this trial have been identified.

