	staff involved, while the negative aspects (such as time for
	the implementation) are to be managed in a supportive
	manner, so the hope is that healthcare managers and staff
	will want to benefit from the intervention, but they will be
	given a free choice as to whether they are willing to commit
	to the trial. Any withdrawals once the trial commences will
	be accepted and records amended to reflect those. It will
	be communicated clearly to those involved in healthcare
	facilities that there are no negative repercussions from
	refusing to participate or withdrawing a healthcare facility
	from the trial.
HCPs may feel over-burdened	The guiding principle for organising data collection activities
with having to provide data or	will be to ensure a minimal additional burden of effort and
	time for HCP staff and service provision. During

Potential adverse effects, discomfort or risks

Steps to be taken to minimize adverse effects, discomfort and risks

help the data collector access register and records.

observations, the data collectors will not intervene in any manner with the conduct of the ANC-PNC visits besides seeking informed consent and giving standardized feedback at the end of the day. All data collection tools are as simplified as possible, so a clinically trained data collector does not need assistance to fill them during observation. In case a specific component needs checking from the patient booklet, the observer will have convened with the HCP of a certain time in the visit to look for specific information (e.g. previous HIV status noted). Observers will have good knowledge of patient documentation to take the shortest time possible. Besides, the programme and intervention is designed to ensure as much as possible that any other type of data needed is already being collected as part of HCP every-day care practices e.g. patient assessment data, routine register data. The sample size (number of women/babies for which data is aggregated) is small with a maximum of 12 observations per step per facility to be performed.

Staff observed or assisting with data collection may not feel comfortable providing information that is likely to cast the health facility's performance in a negative light, for fear that this may have repercussions for them.

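### The stated totals (576–864 women, at most 12 per facility per step) cover one primary outcome, while Box 2 and section 3.7 require that number for each of the two

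*Protocol*

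**What the plan says.** Section 3.4 states: "This trial will have two primary outcomes, one around essential components for ANC, and one for essential components for PNC".

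Two sets of statements then fix the number of observations.

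**Counted per outcome**
- Box 2 (section 3.6) sets at four the "Number of HCP-client interactions assessed for each primary outcome per HCP assessed in an assessment period".
- Section 3.7, under data sources: "In each assessment period there would be a total of 8 to 12 clients per facility for each consultation type". It asks for four consecutive ANC clients per provider and the same for PNC.
- Section 3.6 also says that where only two providers take part, both must accept being observed in ANC and in PNC visits in all four periods.

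**Counted once, with ANC and PNC pooled**
- Section 3.5.3: "Thus, the total number of women asked to consent to be observed will be between 576 and 864".
- Section 3.5.2 expects up to 12 women per facility per step and takes eligible visits until each provider has four.
- Section 3.2.2 counts four interactions per provider, each being an ANC or a PNC visit.
- Section 3.7, under data collection, schedules one observation day per facility per period and says: "All participating HCPs on duty within the HCF will be observed completing four ANC/PNC visits on each of these days".
- Section 3.10 reassures staff about burden with a "maximum of 12 observations per step per facility to be performed".

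The only clinic volumes given are in section 2.1.3, from a survey of 60 facilities in twelve regions: "with 6,936 ANC visits (of which 3,248 attending for the first/booking visit) and 826 PNC visits in the month of the survey".

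**The concern.** The two sets cannot both be followed. A field team working from sections 3.2.2, 3.5.2 and 3.7 (data collection) would stop at four visits per provider, whatever their type. It would then collect half the visits that Box 2 assumes. A team working from Box 2 would observe twice the number of women, and up to twice the number per facility per step, that sections 3.5.3 and 3.10 describe.

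The power statement is also affected. The 0.23 in section 3.6 rests on the mean of four visits per provider for the outcome being analysed. If four visits are shared between two outcomes, each outcome has fewer than four on average. PNC is the rarer visit in the protocol's own survey, so it is the more likely to fall short. A null PNC result could then be read as coming from an adequately powered comparison when it did not.

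**Working it through.** **1. Reproduce the stated total.** Inputs: 18 facilities (section 3.1.1: "All sample size calculation (see relevant sections below) assumed 18 HCFs"), 2 to 3 providers per facility, four visits per provider per period, four assessed periods per facility (Box 2).
- Lower: 18 × 2 × 4 × 4 = 576
- Upper: 18 × 3 × 4 × 4 = 864

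Both match section 3.5.3 exactly. The multiplication is right, but it contains no factor for two outcomes.

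**2. Apply Box 2 and section 3.7 to both outcomes.**
- Total: 2 × 576 = 1,152 to 2 × 864 = 1,728
- Per facility per period: 2 × 8 = 16 to 2 × 12 = 24, against the cap of 12

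Separate clinics do not remove the conflict. Section 3.6 then suggests 4 to 6 providers per facility, and 4 × 4 = 16 to 6 × 4 = 24 visits per period.

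**3. Reproduce the detectable difference.** Section 3.6: SD ceiling √(0.01 + 3 × 0.0225) = √0.0775 = 0.278, and 0.81 × 0.278 = 0.2255, which rounds to 0.23. As a check on the 0.81, I computed the generalised least squares variance for the Figure 1 layout. It used 18 facilities, three per group, eight period effects, a cluster autocorrelation that decays over time, two-sided 5% and 80% power. For ICC 0.5 and CAC 0.1 this gives 0.81, 0.80, 0.95 and 0.90, against 0.81, 0.81, 0.95 and 0.90 in Table 4. Section 3.6 does not state alpha; 5% two-sided is an assumption, in line with the 95% intervals in section 3.8.

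**4. PNC precision by number of PNC visits.** The model has period effects, a training effect, and random effects for facility, provider and facility-by-period. Their SDs are at the protocol's ceiling of 0.15 each (variance 0.0225), with a residual SD of 0.2 per visit (variance 0.04). Detectable difference = (1.960 + 0.842) × SE of the training effect. For the pooled rule, PNC visits per provider-period are drawn as binomial (4, PNC share), averaged over 300 draws.

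| Rule | PNC visits (2 to 3 providers) | Detectable difference (3 / 2 providers) |
|---|---|---|
| Separate quota of four | 576–864 | 0.19 / 0.20 |
| Pooled, 50% PNC | about 288–432 | 0.21 / 0.22 |
| Pooled, 25% PNC | about 144–216 | 0.24 / 0.27 |
| Pooled, 10.6% PNC | about 61–92 | 0.33 / 0.40 |

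The 10.6% is 826 / (6,936 + 826) = 826 / 7,762, so 0.106 × 576 ≈ 61 and 0.106 × 864 ≈ 92. Over the other correlation sets tried, the last row spans about 0.31–0.46. The even split gives 0.23–0.25 at ICC 0.5, CAC 0.1.

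**5. Feasibility of a separate PNC quota.** 826 / 60 = 13.8 PNC visits per facility per month, or 13.8 × 12 / 52 ≈ 3.2 per week, so about 19–22 in a 6–7 week period. That exceeds the 8–12 needed. On an assumed 22 working days a month it is 13.8 / 22 ≈ 0.63 per day, so one arbitrary day would not supply 8–12. If visits were spread evenly, 8–12 would take about 13–19 days.

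**The case against.** The strongest reply is that the passages closest to a sampling specification, Box 2 and the data-source text of section 3.7, set separate quotas, and that the pooled wording elsewhere is loose drafting. No passage says that PNC is left to chance. On that reading 0.23 holds with room to spare (0.19–0.20 in the table). The protocol also leaves slack. Section 3.6 allows a second date within a step and extra visits if numbers are short, section 3.7 allows as many visits as are needed to observe the planned providers, and section 3.5.3 schedules observations from the roster. Average PNC volume over a whole period would cover the quota. Section 3.6 itself warns that shortfalls increase the detectable difference.

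All of this stands, and it rules out some stronger conclusions. A reader might infer that PNC will get only about 60–90 visits and that its 0.23 is lost. That needs three things together: 576–864 covering both types, visits taken in clinic-flow order, and the survey's 10.6% applying to the trial sites. The protocol contradicts the first two in Box 2 and section 3.7. It gives no N'Djamena figure for the third, and a pooled share does not describe facilities with separate PNC clinics.

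A reader might also infer that 72–108 providers are needed (18 × 4 to 18 × 6) against the stated maximum of 54. That is only the upper case in which every site runs separate clinics. Section 3.6 says merely that larger numbers may be preferable at such sites.

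The reply does not remove the mismatch in the counts. If separate quotas are the rule, the consent total and the 12-per-step cap are half of what they should be.

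**Conclusion.** The point holds as an internal contradiction with a consequence for one primary outcome. The total of 576–864 women and the cap of 12 per facility per step fit one outcome. Box 2 and section 3.7 (data sources) require 1,152–1,728 and 16–24. That factor of two needs no assumption about clinic volume.

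The effect on PNC power is conditional. With separate quotas, 0.23 stands. With the pooled rule it is not assured: an even split is close to target, a 25% share misses it slightly to moderately, and the 10.6% share misses it clearly. These figures rest on the protocol's variance ceilings, two-sided 5%, 18 facilities and every planned provider being observed in every period. The contradiction does not by itself call for changing the primary status of the PNC outcome.

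**What to change.** Adopt one sampling rule and state it the same way throughout. The better choice is the rule already in Box 2 and the data-source text of section 3.7: four ANC and four PNC visits per provider per period, with different providers where clinics are separate.

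- Align sections 3.2.2, 3.5.2, 3.5.3, 3.7 (data collection) and 3.10: 576–864 visits per outcome, 1,152–1,728 in total, up to 24 per facility per step.
- Recheck the waiting-time and burden text in section 3.10, which assumes no more than four consultations per provider per day.
- Schedule observation days on PNC clinic days, and do not rely on one general day per period for both types.
- Check the PNC quota against the registers of the chosen N'Djamena facilities. If fewer visits are expected, restate the PNC detectable difference for that number.

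The cost is wording changes, higher stated consent and burden figures that the ethics committee would need to see, probably more observation days, and possibly a less favourable PNC figure. The design, the randomisation and the analysis model do not change.
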